## APPENDIX 6: OFFLOADING

If the ulcer is on the bottom or side of the foot, the subject will be fitted with a standardized off-loading device provided by the sponsor. Off-loading is defined as avoidance of all mechanical stress on the injured extremity and is essential for healing. Avoidance of weight bearing is essential. Trauma causes most plantar ulcers and ongoing trauma prevents healing. Because off-loading (not bearing ANY weight) is so critical to the healing process, subjects will be instructed to wear the RCW at all times except when bathing and to use an RCW at all times when walking or standing is required. Strategies for off-loading will be standardized for all subjects as follows:

All subjects with an ulcer on the bottom of the foot will be fitted with an RCW or other off-loading device during the Screening Visit, according to the following procedure:

- The size of the walker will be determined based on the subject's correct shoe size.
- The appropriate size of the insole will be inserted into the RCW. Once the target ulcer has been debrided, assessed, cleansed, dressed and secured, the RCW will be applied according to the manufacturer's instructions for use.
- The investigator or designee will ensure that the subject and/or family members are able to unfasten, remove and reapply the RCW properly according to the manufacturer's instructions for use.
- Subjects will be instructed to wear the RCW at all times except when bathing or sleeping. When bathing, the subject will be instructed to wear a slipper with a plastic bag worn over the slipper and tied at the ankle or higher.

Subjects will be educated on the importance of using the device to offload their cDFU and instructed on keeping dressings dry. In addition, subjects should be educated on wound infection and if they observe infection to call or visit the study site.

The off-loading RCW/protective device and SOC dressings to be used in this study will be provided by the Sponsor. The off-loading RCW/protective device will only be used by subjects who require offloading throughout the Screening and Treatment (i.e., those subjects with study ulcers located on the plantar or lateral surfaces of the foot or any location experiencing weight-bearing or shear forces as determined by the Investigator). These subjects will wear the RCW up to their exit from the study. The RCW will be applied to the subject's foot after the outer dressings are applied.

# APPENDIX 7: VASCULAR PERFUSION ASSESSMENT

Vascular testing is performed by one of the following methods:

**Screening:** Perform one of the following: ABI (Preferred Assessment) The ABI is the ratio of the brachial pressure (i.e., blood pressure in the arm) to the blood pressure in the ankle. Briefly, the blood pressure is obtained in the arm (brachial) and then obtained in a similar manner in the ankle. To obtain the ratio (i.e., index), divide the systolic pressure from the ankle by that obtained in the arm. ABI is the Systolic Pressure Ankle /Systolic Pressure Arm.

# **Ankle-Brachial Index Technique**

Place the subject in the supine position, with the arms and legs at the same level as the heart, for a minimum of 10 minutes before measurement. Select an appropriately sized blood pressure cuff for both the ankle and the arms (figure 1); the cuff width should be, at a minimum, 20% greater than the diameter of the extremity. The ankle cuff should be placed on the leg between the malleolus and the calf. Enough room should be left below both cuffs to permit placement of the ultrasound gel, so that the Doppler device can adequately detect the brachial, dorsalis pedis, and posterior tibial arteries. Obtain the brachial systolic pressures of both arms. Use the higher of the arm pressures in the ABI calculation. Obtain the pressure in the dorsalis pedis and posterior tibial arteries for the extremity with the target ulcer. Use the highest pressure for the ABI calculation. Ankle-Brachial Index = Highest ankle pressure/ Highest brachial pressure. Care should be taken to cover the ulcer during the ABI measurement. In addition, subjects should be informed that they may experience discomfort during the test secondary to the pressure exerted by the cuff in the area of skin breakdown.

whato roundedon for Medical Education and Research. All lights reserv

# **Arterial Doppler Ultrasound Technique**

Place the subject in the supine position, with the arms and legs at the same level as the heart. Ultrasound gel will be applied to the ankle level to the anatomic position of the dorsalis pedis and posterior tibial vessels. The Doppler will then be applied to each vessel until a waveform is established, a printer will be used to document the Doppler waveform and at least three waveforms will be printed for each vessel and filed with source. The clinician will verify biphasic or triphasic waveforms.

# Transcutaneous Oxygen Level (TcPO2)

TcPO2 is a measure of oxygen delivery to a local area. A special machine must be used to assess TcPO2. Briefly, electrodes for the sensor will be placed onto the intact skin close to the study ulcer. The oxygen sensor then can read the oxygen content of the tissue and reports this as mmHg pressure. Each site should refer to the equipment's manual for specific and correct instructions for use. For this study, potential study candidates must have a TcPO2 greater than 40 mmHg.

Technique: Place the subject in the supine position, with the arms and legs at the same level as the heart. Electrodes must be in contact with the tissue through the contact liquid. If there is air between the tissue and an electrode, TCOM values will be questionable. Erroneous readings may also occur if electrodes are placed directly over a bone or there is severe edema around the wound. For best results, tests should be conducted at ambient temperature (21-23° C), and the subjects should not have smoked nor had caffeine for several hours prior.

- 1. Calibrate the TCOM electrode—this takes about 15-20 minutes.
- 2. Clean the selected measuring site with alcohol or other skin-preparation solution.
- 3. Dry the site well with a gauze pad.
- 4. Take a standard fixation ring.
- 5. Remove the fixation ring from the protective film.
- 6. Apply the fixation ring to the measuring site as follows: Press the center of the fixation ring onto the measuring site with a finger. Run a finger around the rim circumference. Press firmly to prevent leaks.
- 7. Fill the hole in the fixation ring with 3-5 drops of the contact liquid.
- 8. Affix the electrode into the fixation ring as follows: Align the arrow on the electrode with one of the marks on the fixation ring. Turn the electrode 90° clockwise to fasten it in the fixation ring.
- 9. Repeat steps 1 to 8 if more electrodes are to be applied; note: several electrodes can be calibrated at the same time.

It is sometimes advantageous to simultaneously use several electrodes placed strategically around the wound and calculate mean values from individual readings. The normal sequence of events for TCOM is measurement in air, the leg elevation test (optional), and the oxygen challenge. The optimal times for these events in terms of measurement time are, 20, 5, and 10 minutes, respective

**Table 1. Version History** 

Version Number	Release Date	Change(s)	Reason for Change
1.0	April 5, 2022	N/A	Initial Release

SAP: LLA-Nu3-CLIN002 Page 3 of 21

# **Brief Trial Description**

This study is a phase 2a, multi-center, double-blind, placebo-controlled, dose-escalating, parallel group, randomized controlled trial designed to evaluate the safety and tolerability of topically applied bisphosphocin NU-3 gel to clinically non-infected Wagner grade 1 diabetic foot ulcers (DFUs).

Two weeks after screening, subjects will be randomized 3:1 to bisphosphocin Nu-3 gel and standard of care (SOC) or placebo gel and SOC to treat Wagner 1 DFUs. Major inclusion criteria will be DFUs between 1.0 and 10 cm^2 initial area and having no wound ischemia.

Subjects will be seen weekly until 6 weeks after randomization unless the subject's wound healed, or the subject is withdrawn or lost to follow-up (i.e., early termination). The bisphosphocin Nu-3 or placebo gel will be applied starting on the day of randomization for 4 weeks twice daily. The study will be executed in two phases: cohort 1 and cohort 2, in which the doses for the intervention group will be 5% or 10% Nu-3 gel.

SOC in this study will be offloading of the DFU using a removable cast walker provided to the subject, appropriate sharp or surgical debridement (note: there will be several rules pertaining to prohibition on certain visits and degree of debridement), and infection management post-randomization as deemed appropriate by the investigator. Primary dressings will be Mepitel (or equivalent), Tegaderm, and padding/Coban Lite 2- layer dressing.

#### General

Descriptive statistical methods will be used to summarize the data from this study. These include number of subjects (n), mean and standard deviation (SD) for continuous variable data (medians and IQR [interquartile range] values will be given when the distribution of variable values is non-normal), and frequencies and percentages for categorical variable data. There will be no hypothesis testing performed. All data collected during the study will be reported and analyzed.

Unless specified otherwise, all statistical testing will be two-sided and performed using a significance (alpha) level of 0.05.

All statistical analyses will be conducted using PASW 27 (SPSS; IBM).

#### **Sample Size Calculations**

Since this is a pilot study focusing primarily on safety, no sample size calculations will be done. Based on general experience with phase 2a trials, it is planned to enroll 32 subjects (24 active and 8 placebo).

## Randomization

Subjects eligible for the study after screening and run-in will be randomized 3:1 to bisphosphocin Nu-3 gel and SOC or placebo gel SOC.

#### **Interim Analysis**

SAP: LLA-Nu3-CLIN002 Page 4 of 21

A safety review will be conducted by an independent Data Monitoring Committee (DMC) after the first cohort to confirm it is acceptable to proceed to the next dose level.

# **Trial Stopping Rules**

Subjects will be permitted to withdraw at any time and investigators can withdraw a patient based on the occurrence of an AE/SAE interfering with treatment or placing the subject's health in jeopardy, or pause treatment for any one these scenarios: (a) wound gangrene; osteomyelitis; G3-4 AE; SAE related to study drug. Occurrence of ≥3 of the above criteria in any given cohort will also require a pause in treatment for the cohort, with subsequent actions determined based on the DMC charter.

## **Patient Populations**

The populations defined for the final analysis include intent-to-treat (ITT), modified-intent-to-treat (MITT), per protocol (PP), and safety populations are defined as shown in Table 2. All the defined populations will be analyzed unless the populations are the same; for example, if no subjects were withdrawn, lost to follow-up, or died, and all subjects received assigned doses, then the ITT and MITT groups would be identical and MITT analysis would be dropped.

Variable	Intent-to-treat (ITT)	Modified- intent-to-treat (MITT)	Per Protocol (PP)	Safety (SP)
All randomized subjects	✓			
Analysis per assigned treatment group	✓	\		\
Major protocol violation	\	\		\
Withdrawn, died, or lost to follow-up	✓			\
Received at least one treatment	✓	✓		✓
Received at least 80% of doses			✓	
Received no treatment	1			

SAP: LLA-Nu3-CLIN002 Page 5 of 21

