## Title of Study:

A PHASE 2a, MULTI-CENTER, RANDOMIZED, DOUBLE-BLIND, PLACEBO-CONTROLLED DOSE ESCALATING STUDY TO EVALUATE THE SAFETY AND TOLERABILITY OF TOPICALLY APPLIED BISPHOSPHOCIN® NU-3 GEL TO CLINICALLY NONINFECTED CHRONIC DIABETIC FOOT ULCERS (cDFU)

Study center(s): up to 5 sites

**Subject Population:** Male and female subjects age 18 years of age or older and up to and including 80 years of age suffering from diabetes mellitus and cDFU

Sample Size: Maximum of 32 subjects, 24 active and 8 placebo

**Examination Points:** Screening Day - 14, Standard-of-Care (SOC) Run-in Day - 7, Baseline Day 0, Day 7, Day 14, Day 21, Day 28 (End of Treatment/EOT) and Safety Follow-up Day 42 from first treatment. All visits are to be completed within a visit window of  $\pm$  2 days.

Study Design: Multi-Center, Randomized, Double-Blind, Placebo-Controlled, Dose Escalation Study

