#### **Test Kit**

Test Product kits will contain eighteen (18) 4 gm applicators of Test Product packaged individually in foil pouches. The kits and individual 4g applicators will be pre-labelled with kit numbers. The contents of the kits will not be known to any site personnel. Upon randomization of the subject through a centralized randomization service, the site personnel will receive a randomization number along with a kit number that is available at that site. The kit will be used for dose administration twice daily for one week. A new Test Product Kit will be dispensed to the subject at each of the subsequent visits on Days 7, 14, and 21.

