## **Statistical Analysis**

Summary tables (descriptive statistics and/or frequency tables) will be provided for all baseline variables, efficacy variables, and safety variables. Continuous variables will be described by descriptive statistics (n, mean, standard deviation, minimum, maximum, median, 95% confidence limits for the mean) as detailed in the statistical analysis plan.

Frequency tables will be used to report adverse event frequency by system organ class (SOC), preferred term (PT), severity, and relationship to test article. All subjects receiving the test article will be included in the safety analyses.

Safety data including laboratory evaluations and vital signs assessments will be summarized by dose group and time point of collection. Descriptive statistics will be calculated for quantitative safety data, and frequency counts will be compiled for classification of qualitative safety data. In addition, a mean change from baseline table will be provided for vital signs and a shift table describing out of normal range shifts will be provided for clinical laboratory results.

Changes in physical examinations will be described in the text of the final report.

Efficacy data including clinical and microbiological response will be summarized by dose group and will include analysis per the statistical analysis plan.

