# 4. OJECTIVE AND ENDPOINTS

	Objective	Endpoint [at 28 days]	Variable			
Primary	•To assess the safety and tolerability of escalating doses of topically applied Bisphosphocin Nu-3 Gel	Treatment emergent events related to clinical investigational product	
 
Vital signs
 
Safety laboratory analysis
 
Local wound/skin assessments
 
Physical examination
 
Adverse events
 
			
Secondary	
 
To assess the clinical effects of Nu-3 on cDFU
 
To assess antimicrobial effects of Nu-3 on wound microflora.
 
To support determination of the appropriate dose range of Nu-3 to be employed in future clinical studies.
 
	
 
Advanced digital imaging wound assessment post debridement
 
Pre and Post debridement digital pictures taken by clinical staff.
 
Changes in wound microbial population pre debridement
 
Recommended Phase 2 Dose (RP2D)
 
	
 
Ulcer surface area
 
Ulcer depth
 
Culture and microflora microbiological analysis
 
			

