# **Analysis**

The following analyses will be conducted:

- Flow chart (subjects) with disposition according to CONSORT criteria. (see shell Figure 1).
- Overall trial statistics (enrollment dates, site numbers, numbers of subjects, group assignments)
- Withdrawals (including death), and loss to follow-up (total and by group assignment) with week of discontinuation and reason.
- Screen failure rate and screen failure reasons according to exclusion criteria

SAP: LLA-Nu3-CLIN002 Page 7 of 21

Demographics between groups at baseline (subject-related and wound-related variables): patient age, smoking/alcohol status, BMI, HbA1c, creatinine levels; diabetes duration); number of concurrent DFUs, prior DFUs and amputations, history of DFU recurrence, history of and significant foot deformities (if available); DFU location, ulcer duration, initial area; baseline variables between groups will be tested using t tests, Mann-Whitney, chi square, and Fisher exact tests (as appropriate) without adjustment for multiplicity testing (see shell Tables 1 and 7).

- Subject comorbidities will be listed using first-level medDRA organ classes by treatment group (see shell Table 8); for each subject the total number of comorbidities will be calculated and then the means between groups will be tested in the same way as for demographics and added to shell Table 1
- Prescription medications will be listed using WHODrug classes by treatment group (see shell Table 9); for each subject the total number of prescription drugs will be calculated and then the means between groups will be tested in the same way as for demographics and added to shell Table 1
- The primary endpoint analysis will be a summary of the incidence of treatmentemergent adverse events (TEAEs), including subject and overall AE rates by treatment group:
  - Summary statistics for each treatment group (count of TEAEs per group/per patient; summary rates per group; notes of unexpected occurrences during the study; relevant decisions made) [text in report]
  - SAE (brief description; resolution; impact on study (e.g., withdrawal, etc.) [text in report]
  - All TEAEs by system organ class (SOC), preferred term (PT), severity, and relationship to test article (see shell Table 10).
- Other safety data will be analyzed as follows:

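### The SAP appears to analyse the Safety population by assigned arm, with no rule for attributing adverse events to the product actually received

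*SAP*

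**What the plan says.** SAP, Patient Populations, Table 2 sets out four populations. The row "Analysis per assigned treatment group" is marked for ITT, MITT and Safety and is blank for per protocol. The Safety column is also marked for "Received at least one treatment" and for "Major protocol violation". A subject therefore enters the Safety set by exposure, stays in it after a major violation, and is placed in an arm by randomization.

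The Protocol synopsis (Statistical Analysis) states: "All subjects receiving the test article will be included in the safety analyses". It then groups safety data by dose group, without saying whether that means assigned or received. The SAP Analysis section speaks only of treatment group or dose group.

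Safety is the main purpose of the trial. Protocol section 4 gives the primary objective as "To assess the safety and tolerability of escalating doses of topically applied Bisphosphocin Nu-3 Gel". The SAP Analysis section says "The primary endpoint analysis will be a summary of the incidence of" TEAEs, by treatment group.

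On supply, the Protocol synopsis (Test Kit) has a first kit issued at randomization and then says: "A new Test Product Kit will be dispensed to the subject at each of the subsequent visits on Days 7, 14, and 21". Protocol section 7.5 keeps kit contents unknown to the pharmacist, clinical staff, CRO and sponsor.

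**The concern.** Analysis by assigned arm protects a randomized efficacy comparison. A harms table has a different job: it should show which product the affected subject was exposed to. Under the rule as written, a placebo-assigned subject who is given an active kit and then reacts counts as a placebo case. This raises the placebo rate and removes a case from the active arm, in a table with only 8 placebo subjects.

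The SAP allows for the possibility. Its example for dropping the MITT analysis depends on all subjects having received their assigned doses. It gives no safety attribution rule for the case where they did not. Because contents are blinded, a wrong product would not be recognised from the kit at dispensing. It would emerge when kit numbers are reconciled with the randomization list.

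**Working it through.** **Reading the table.** In the extracted text the Safety cell of the assigned-arm row shows a backslash, not the check mark seen in some other cells. The same backslash stands in the ITT column for major protocol violations, a group that ITT must include. Cells meant to be empty are blank. The backslash is therefore almost certainly a damaged tick. A look at the SAP's PDF will settle it.

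**Search for a correcting rule.** The places that could hold one are the Protocol synopsis (Statistical Analysis, Analysis Populations), Protocol section 12 and the SAP Analysis section. None assigns a subject to the product received.

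**Inputs.** The Protocol synopsis gives the size as "Maximum of 32 subjects, 24 active and 8 placebo", in two cohorts of 12 active and 4 placebo. Check: 2 × 12 = 24, 2 × 4 = 8, total 32. Each subject who completes treatment receives four kits (Days 0, 7, 14 and 21). The plan states no error rate or misattribution figure that could be reproduced.

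**Size of one misattribution.** One placebo-assigned subject with an event is 1/8 = 12.5 points of the placebo rate.

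Illustration with assumed counts: 2 of the 12 subjects assigned 5% gel have a TEAE. One placebo-assigned subject received 5% gel and also has one. No other placebo subject does.

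| Attribution | 5% arm | Placebo | Difference |
|---|---|---|---|
| As assigned | 2/12 = 16.7% | 1/8 = 12.5% | 4.2 points |
| As received | 3/13 = 23.1% | 0/7 = 0% | 23.1 points |

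**Which dispensings can matter.** Suppose a subject with mixed exposure is grouped under the highest concentration received.
- An active subject given one placebo kit stays in the same arm. So does a 10% subject given one 5% kit.
- A 5% subject is unlikely to be given a 10% kit, because the cohorts are sequential and the escalation review falls in the safety follow-up, after dosing (Protocol sections 5.1 and 7.3).
- This leaves the placebo dispensings: 8 subjects × 4 kits = 32.

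**Chance of at least one wrong kit among those 32.** The documents give no error rate q, so q is assumed, with independent errors: P = 1 − (1 − q)^32.

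| Assumed q | P |
|---|---|
| 0.25% | 1 − 0.9975^32 = 7.7% |
| 0.5% | 1 − 0.995^32 = 14.8% |
| 1% | 1 − 0.99^32 = 27.5% |

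These are upper bounds on the chance of a misattributed event, for two reasons. A wrong kit may also be placebo: if it were a random draw from 3:1 stock (a further assumption), 75% of wrong kits would be active, and 1 − (1 − 0.75q)^32 gives 5.8%, 11.3% and 21.4%. The subject must also have a TEAE.

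**The case against.** The case against giving this much weight has several parts.

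- **No error is reported, and controls exist.** A central system issues a kit number matched to site stock (Protocol section 7.5), and each kit is collected and accounted for at the next visit (sections 7.6 and 8). If no subject receives another arm's product, both rules give identical tables. This stands, and it makes the harm conditional.
- **The narrative may catch it.** The primary summary is descriptive, reports relationship to test article and includes notes of unexpected occurrences. A kit error followed by a local reaction could be described there. This softens the consequence, but the tabulated rates would still be wrong.
- **Grouping by highest concentration has its own bias.** One wrong weekly kit would move all of a placebo subject's events to active, including those that began earlier. This stands, and it is why the fix needs onset dates.

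A reader might also infer more than the documents support:

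- **All 32 × 4 = 128 dispensings are at risk.** At the same assumed rates this would give 27%, 47% and 72%. But 24 × 4 = 96 of them go to active subjects, where a single wrong kit would essentially not change the arm under the grouping above.
- **A dose arm could lose 1/12 = 8.3 points.** That needs an active subject who received no active kit at all.
- **Dose selection is compromised.** The data monitoring committee decides on escalation from dose-limiting toxicity criteria in a separate charter, and nothing says that it works from this SAP table. The pause rule counts events per cohort, not per arm, so attribution does not alter it.

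**Conclusion.** The concern holds as a defect in a stated rule with a conditional consequence. On the likely reading of Table 2, the Safety population is analysed by assignment, and nothing in either document overrides that. Followed as written after a placebo subject received active gel, the rule would put that subject's later events in the wrong column of the primary safety table, at 12.5 points of the placebo rate per such subject.

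The chance that this arises is modest: at most about 8% to 27% over assumed error rates of 0.25% to 1% per dispensing, and lower once placebo-for-placebo errors and the need for a TEAE are counted. The conclusion rests on reading the damaged mark as a tick, on those assumed rates with independent errors, and on all placebo subjects receiving four kits. It does not show that any event has been misattributed. The correction is worth making because it costs almost nothing and is best settled before anyone knows of a mismatch.

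**What to change.** In SAP Table 2, remove the assigned-arm mark for the Safety population and state that it is analysed by product actually received, taken from kit accountability records. Keep assigned-arm analysis for ITT and MITT.

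Add a sentence for mixed exposure: a subject who received more than one product is grouped under the highest concentration received. Add a listing of every mismatch between assigned and received product, with kit dates and adverse event onset dates, so that events starting before the wrong kit are visible as such.

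The cost is one table cell, one or two sentences and one listing. Kit numbers and returns are already recorded under Protocol sections 7.5, 7.6 and 8. The change should be made before database lock and unblinding, because choosing the attribution rule once a mismatch is known would be data-driven.
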